20.5 Inclusion in analysis

All randomised participants will be included in the primary intention-to-treat population and they will be analysed as randomised regardless of intervention received.

A per protocol population will be defined in the statistical analysis plan and will be analysed to provide supplementary evidence in support of the primary analysis.

20.6 Subgroup analysis

Subgroup analyses of patients by pathological tumour stage will be undertaken to understand the potential difference in outcomes seen with surveillance in more advanced tumour stages.

20.7 Interim analyses

Given the nature of the primary outcome and the planned study length, no formal comparative interim analyses are planned. However, accumulating data will be reviewed regularly by the Data

Safety and Monitoring Committee (DSMC), including reviewing data by treatment arm and patient safety.

20.8 Stopping Rules

There are no formal stopping rules planned.

20.9 Level of Statistical Significance

5% significance will be used throughout and differences between the intervention arms will be reported using 95% confidence intervals.

20.10 Procedure for accounting for missing, unused and spurious data

The procedure for handling spurious or missing data will be described in the SAP. The trial will attempt to collect data as completely as possible. There will be no missing data for the primary outcome as patients who have not died will be censored at their last known alive date and therefore included in the analysis.

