9.2 Primary objective and outcome measure

Objective	Outcome measure	Time point(s) of evaluation of this outcome measure (if applicable)	Data required	Source data (including location)
To assess whether intensive surveillance, including radiological investigations and an endoscopic investigation after completing curatively intended treatment, improves survival in patients with oesophageal or gastric cancer.	All-cause mortality defined as death from any cause. Participants who have not been observed to die during the course of the study will have their survival time censored at their last known follow-up date.	3 years post- randomisation of the last included participant.	Date of randomisation. Date of death. Date last known alive if not dead.	Participant's medical notes.

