10.6 Use of NHS England data (including data from registries)

The NOGCA is commissioned by the Healthcare Quality Improvement Partnership (HQIP) as part of the National Clinical Audit and Patient Outcomes Programme (NCAPOP). The data processes and validation of the entered data has been well established for patients receiving surgery for oesophageal and gastric cancer since 2012. This national audit is used by all oesophago-gastric specialist cancer centres in England and Wales for the entry of oesophageal and gastric cancer patients undergoing treatment both curative and palliative.

Participants from the SARONG study will be consented for linkage of their data to the Office of National Statistics (ONS) and NOGCA datasets. Locally collected data from participant medical records will be checked against mortality data from ONS, and from NOGCA.

Patients that decline to take part in the study will continue to have their data collected as part of their normal clinical surveillance and recorded within NOGCA. Data will also be collected regarding

additional radiological and endoscopic imaging during surveillance, to evaluate if a change in surveillance protocols has been observed within participating centres during the study, in non-study participants. Thus, the external validity of the study findings will be tested through comparison of the SARONG study data, with NOGCA data from non-participating patients and centres.

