14.2 Usual care (comparator/control)

Participants randomised to the comparator arm will receive standard care follow-up following their surgery. Standard care comprises of a clinical review at 6 and 12 months and after 12 months, participants are either discharged to primary care or clinically reviewed annually by the treating centre, with targeted investigations as needed. Targeted investigations are recommended in the event of new onset alarm symptoms (see section 14.2.1 below).

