20.2 Sample Size/Power calculations

We aim to recruit 952 participants over 32 months from at least 24 NHS centres. Data from the ENSURE study [15] indicated all-cause mortality rates in the standard-of-care arm of 55% at 3-years. Based on discussions with clinicians and patient representatives, a 10% absolute improvement in overall survival would be clinically meaningful to patients and would lead to change clinical practice. An absolute improvement in survival of 10% was also used in the recent CROSS and Neo-AEGIS trials [5,25]. The sample size calculations were based on a comparison of the survivor functions in the two groups using a two-sided log-rank test. The sample size was calculated based on statistical power of 90%, two-sided alpha=0.05 with a 3-year recruitment period and 3-year follow-up period and an expected all-cause 3-year mortality in the control group of 55% and an assumed improvement to 45% in the intervention group. This correspond to a hazard ratio of 0.749, assuming hazard rates are proportional. Allowing for a 10% loss to follow-up based upon average estimates from MAGIC and OEO2 trials in the UK [26, 27], 952 patients would need to be recruited to this trial, with approximately 273 all-cause mortality events occurring in the control arm and 229 events in the intervention arm.

Since the proposed translational sub-studies are intended to be hypothesis generating, no formal sample size calculations have been performed.

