20.4 Description of Statistical Methods

Results will be reported in line with the CONSORT statement.

All analyses will be carried out on the intention-to-treat population (i.e. all patients will be analysed in the group that they were randomised to regardless of the actual treatment received). It is not anticipated there will be any protocol deviations, however, in the event that any occur, we will

repeat the primary analysis for the per protocol population (patients excluded from the per-protocol population will be pre-specified in the SAP).

Standard descriptive statistics will be used to describe the demographics between the two follow-up regimens; reporting means and standard deviations or medians and inter-quartiles ranges as appropriate for continuous variables and numbers and percentages for binary and categorical variables. All comparative outcomes will be presented as summary statistics and reported together with 95% confidence intervals. All tests will be carried out at a 5% significance level.

It is anticipated that all statistical analysis will be undertaken using Stata (StataCorp LP, www.stata.com) or other well validated statistical software.

Primary outcome

The primary outcome is overall survival. An event is defined as death from any cause. Participants who have not died during the trial will have their survival time censored at their last known alive date. This includes participants who withdraw from the trial.

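### Survivors are censored at a contact-dependent last known alive date while deaths are also checked against registries, with no common vital-status date, so the primary hazard ratio can be biased in either direction

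*Protocol*

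**What the plan says.** **Censoring rule.** Section 20.4: "Participants who have not died during the trial will have their survival time censored at their last known alive date", withdrawals included. Section 20.10 repeats this, saying that "patients who have not died will be censored at their last known alive date", and infers that no primary-outcome data will be missing. Section 9.2 lists "Date last known alive if not dead" among the data required and gives the participant's medical notes as the only source for that row. The Synopsis and the outcome definition in 9.2 speak of the last known follow-up date instead.

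**Deaths.** Section 10.2 collects mortality from the medical record and validates it against NOGCA and ONS, with discrepancies taken back to the site to establish the correct data. Section 10.6: "Locally collected data from participant medical records will be checked against mortality data from ONS", and from NOGCA. Section 21.1 repeats the check every 6 months. Section 10.3 names NCRAS where the other sections name ONS. Section 17.3.1 asks withdrawing participants to allow continued use of records, ONS and NOGCA for the primary mortality analysis.

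**Contact.** Intervention participants have clinic or telephone review and CT every 6 months to month 36. For controls, section 14.2 says that after 12 months "participants are either discharged to primary care or clinically reviewed annually by the treating centre". Sections 17.1 and 17.2.2 schedule outcome data collection and questionnaires every 6 months to month 36 in both arms.

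**Horizon.** The Synopsis gives mortality at 3 years post-randomisation. Sections 9.2 and 10.3 run mortality collection until 36 months after the last randomisation.

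**The concern.** Censoring is harmless when the date at which follow-up stops does not depend on whether the participant later dies. Here it may. A death that is absent from the hospital notes but present in the registry is a discrepancy. The site verifies it, and it is then dated correctly. A survivor with no recent hospital entry produces no discrepancy, and no section says that the absence of a death record confirms the person alive to the extract date. That survivor leaves the risk set at the last contact, while someone with the same contact history who dies stays in it until death. The late hazard is then overstated.

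If this happens more often in controls, whose clinic contact may end at 12 months, the control hazard rises and surveillance looks better than it is. After month 36 neither arm has scheduled contact but deaths are still collected. In that period the risk set consists mostly of people who are going to die, in both arms, and a true difference is diluted. At stake is the primary hazard ratio of an open-label trial whose arms differ in contact by design.

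**Working it through.** **1. The design figures reproduce.** Section 20.2 uses "two-sided alpha=0.05 with a 3-year recruitment period and 3-year follow-up period", 90% power, and an "expected all-cause 3-year mortality in the control group of 55% and an assumed improvement to 45% in the intervention group".
- HR = ln(0.55)/ln(0.45) = 0.5978/0.7985 = 0.749, as stated.
- Events (Schoenfeld) = 4 × (1.960 + 1.282)² / (ln 0.7487)² = 42.03/0.0838 ≈ 502. The protocol's 273 + 229 = 502.
- With exponential survival, uniform 3-year accrual and the 10% loss read as 10% per year, N = 950 (stated 952), and 476 per arm gives 273.6 and 229.5 events. The protocol does not give the time base of the 10%.

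The design is internally sound, and it already assumes that some follow-up will be lost.

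**2. Hand check of the mechanism in the control arm.** Let f be the fraction of control survivors last known alive at 12 months, with all deaths known. The documents give no value for f, so it is an assumption. Take exponential survival with S(3) = 0.45, so S(1) = 0.45^(1/3) = 0.766. The survivors removed at 12 months are 0.45f. The Kaplan-Meier estimate at 3 years becomes 0.766 × 0.45(1 − f)/(0.766 − 0.45f).
- f = 10%: 0.766 × 0.405/0.721 = 0.430, so mortality reads 57% instead of 55%.
- f = 20%: 0.766 × 0.360/0.676 = 0.408, so mortality reads 59%.

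**3. Effect on the hazard ratio when the true HR is 1.** Unadjusted Cox models were fitted to simulated data: control hazard −ln(0.45)/3 in both arms, all deaths at their true dates, a fraction f of control survivors censored at 12 months, and every other survivor in either arm censored at month 36. Large samples give the HR; trials of 476 per arm give the two-sided type I error. Two horizons are shown because the Synopsis and sections 9.2 and 10.3 differ.

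| f (assumed) | HR, deaths to 36 months | Type I error | HR, deaths to calendar end | Type I error |
|---|---|---|---|---|
| 0 | 1.00 | 5% | 1.00 | 5% |
| 5% | 0.98 | about 6% | 0.98 to 0.99 | about 4 to 6% |
| 10% | 0.96 | about 8% | 0.97 to 0.98 | about 6% |
| 20% | 0.91 | about 19% | 0.95 to 0.96 | about 10 to 11% |

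Ranges reflect simulation variation.

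**4. Controls on the mechanism.** With f = 20% in both arms the HR is 1.00. If deaths and survivors alike are censored at 12 months in 50% of controls, it is also 1.00. The bias therefore needs both ingredients: deaths followed further than survivors, and a difference between arms.

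**5. Effect when the design HR of 0.749 is true.**
- To 36 months: about 0.75 at f = 0 and about 0.68 at f = 20%.
- To calendar end (32 + 36 = 68 months for the first participant), with survivors last known alive at month 36: about 0.79 at f = 0, which is towards the null, and about 0.74 at f = 20%.

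**6. The no-missing-data statement.** Section 20.10 says none will be missing; section 20.2 allows for 10% loss to follow-up. Censoring keeps a participant in the analysis but does not supply the unobserved follow-up.

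**The case against.** A reader might infer that deaths are completed from ONS while survivors are not, and that the hazard ratio is therefore bound to favour surveillance. The documents do not support that.

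- **Registry role.** The words used are validation and checking, and 9.2 gives medical notes as the source for death and alive dates alike. That registry-only deaths enter the data is inferred from the discrepancy process in 10.2 and the withdrawal text in 17.3.1. It is a reasonable inference but not a stated rule.
- **Contact in both arms.** Outcome collection and questionnaires run every 6 months to month 36 for everyone. There are two reminders, a status check with the site and a telephone attempt (17.2.2). This can supply alive dates for discharged controls, and it stands as a real mitigation. It is not a guarantee: site data may come from notes alone, section 17.4 says only that non-responders may be telephoned, participants may stop questionnaires while leaving registry access open (17.3.1), and 9.2 does not list questionnaires as a source for the primary outcome.
- **Size.** A value of f = 20% needs, for example, half of controls discharged and 40% of those yielding no later alive date, while every intervention survivor is known alive at month 36. Nothing in the protocol supports that contrast. At 5% the type I error is close to nominal.
- **Direction.** Loss of contact after month 36 pulls a true benefit towards the null, so the net direction is open.
- **Left to the SAP.** Section 20.10 defers missing-data handling to the SAP, and a data cut-off date is commonly set there. But the protocol itself fixes the censoring rule in several places, and a SAP with a common date would have to depart from it.

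**Conclusion.** The concern holds as a risk, not as a demonstrated bias. The protocol fixes a censoring date that depends on contact, provides registry checks for deaths only, and sets no common vital-status date.

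The size rests on two assumptions: that registry-identified deaths enter the analysis, and the value of f. With 5 to 20% of control survivors affected and no true effect, the HR lies between about 0.98 and 0.91 to 36 months, and between about 0.99 and 0.95 to calendar end. Without any difference in contact, a true 0.749 reads about 0.79 to calendar end if survivors are last known alive at month 36. Bias in either direction is possible, so a certain false benefit for surveillance should not be claimed.

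The statement that no primary-outcome data will be missing is wrong whatever f is. The rule should be settled before data lock; the planned 502 events and N = 952 are unaffected.

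**What to change.** Amend sections 9.2, 20.4 and 20.10, and align the Synopsis wording:

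1. Set one vital-status cut-off date, applied identically to deaths and survivors in both arms: the completeness date of the registry extract, or 36 months after the last randomisation if that is earlier. Do not count deaths after it.
2. Censor at that date participants who are confirmed as linked and have no death record.
3. For participants who refuse linkage, cannot be linked or fall outside registry coverage, use the last known alive date from any source (notes, questionnaires, status checks) and report their number by arm.
4. Keep last-known-alive censoring for everyone as a sensitivity analysis.
5. Replace the no-missing-data sentence with a statement that early censoring is incomplete follow-up and will be reported by arm.
6. Reconcile NCRAS in 10.3 with ONS in 10.2, 10.6 and 21.1.

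**Cost.** Linkage and consent for it are already planned (10.6), so this is mainly wording plus confirmation of linkage status for each participant. The downside is reliance on linkage completeness: a death missed by linkage would count as survival. Section 10.6 describes NOGCA for England and Wales, recruitment is UK-wide, and 20.13 holds Scandinavian sites in reserve, so the fallback in step 3 is needed.

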20.11 Procedures for reporting any deviation(s) from the original statistical analysis plan

Any changes or deviation from the original SAP will be described and justified in the final report and/or publications, as appropriate.

20.12 Health economics analysis

A cost-effectiveness analysis will be conducted by the health economists at the University of Oxford.

We will conduct a within trial cost-utility analysis to assess the cost-effectiveness of implementing an intensive structured follow-up after oncological treatment compared with current practice. As described above, the structured follow-up includes clinical reviews, CT scans and endoscopy for up to 36 months whereas current practice consists of clinical symptomatic follow-up.

We will use an NHS and Personal Social Services perspective for the base-case analysis and a societal perspective will be presented in the sensitivity analysis [30,31]. The primary outcome measure used in the health economics study will be the incremental cost per QALY. We will follow good practice guidelines when undertaking the economic evaluation analysis [30-32].

Data on resource use will be collected for healthcare (primary care appointments, prescribed and over the counter medications, hospital admissions, contact with healthcare professionals) and non-healthcare resource use (social and informal care, and time off work) of patients undergoing the two arms of trial. The questionnaire will be administered at baseline (4-8 weeks after surgery), 6, 12, 18, 24, 30 and 36-months post-randomisation. The resources used will be valued using national cost databases such as NHS Reference costs and Prescription Cost Analysis.

The EQ-5D-5L instrument [33] will be used to measure HRQoL at baseline (4-8 weeks after surgery), 6, 12, 18, 24, 30 and 36-months post-randomisation. The EQ-5D-5L instrument will be valued using NICE recommendations at the time of the analysis, either using a UK value set or converted into the EQ-5D-3L using a cross-mapping algorithm [34] and valued using the UK set for EQ-5D-3L [35]. QALYs will be calculated using the area under the curve approach, which involves estimating the average EQ-5D utility between each follow-up time, and weighting it by survival time. We will report descriptive statistics (means, SD as a minimum) for healthcare resource use, costs, and EQ-5D utilities at each follow-up time point.

We will test for baseline difference in healthcare resource use and utilities between the trial arms and if required adjust for these differences using the most appropriate recommended method [36]. All costs and effects will be discounted at 3.5% following NICE guidelines.

We will follow best practice methods for addressing missing data in cost-effectiveness studies [37]. Missing data on participant characteristics at baseline will be imputed following guidelines. Incremental cost effectiveness ratio (ICER; cost per QALY) will be estimated by dividing the difference in costs by the difference in QALYs of the two treatments under analysis and will be depicted on the cost-effectiveness plane. The ICER will be compared against the threshold used to establish value for money in the NHS (currently in the region of £20,000 to £30,000 per QALY) [30]. We will estimate the joint uncertainty around incremental costs and QALYs and in cost-effectiveness using a bootstrapping approach take accounts for the imputed data. From these bootstrapped results, we will calculate the probability that the intensive structured follow-up for up to 3 years after oncological treatment is more cost-effective than the current practice led by clinical symptomatic follow-up for different threshold values per QALY gained [38]. These will be calculated by estimating the proportion of bootstrap replicates with a net monetary benefit (NMB) above 0 for each threshold value, where the NMB is given by the product of the mean difference in QALYs and the threshold value minus the mean difference in costs.

The robustness of results will be evaluated in a sensitivity analysis.

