10.3 Duration of participant involvement

Participants will be in the study for approximately 36 months from randomisation to last protocol visit. Mortality and recurrence data will be collected for 36 months after the last participant is randomised, this data will be collected from medical records and in the case of all-cause mortality validated against NOCGA and NCRAS.

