10.7 Health Economics

A cost-utility analysis to assess the cost-effectiveness of implementing an intensive surveillance after oncological treatment compared with current practice will be conducted.

Participants will be asked to complete a resource use questionnaire which will collect healthcare (primary care appointments, prescribed and over the counter medications, hospital admissions outside of their participating institution, contact with other healthcare professionals) and non-healthcare resource use (social and informal care, travel costs and time off work) of participants in both arms of study. The questionnaires will be administered to patients at baseline and at 6, 12, 18, 24, 30 and 36-months post-randomisation. Secondary care resource usage at the participating institution will also be collected from the participant's medical records.

The EQ-5D-5L instrument will be used to measure HRQoL at baseline and at 6, 12, 18, 24, 30 and 36-months post-randomisation.

Refer to section 20.12 for full details of the health economic analysis.

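### The only economic horizon fixed is 36 months, so at the design effect much of the survival gain probably goes uncounted and the ICER is likely, though not certainly, overstated

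*Protocol*

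**What the plan says.** Section 20.12 of the protocol sets the horizon: "We will conduct a within trial cost-utility analysis to assess the cost-effectiveness of implementing an intensive structured follow-up". The data behind it end at month 36. Section 10.7 says "The EQ-5D-5L instrument will be used to measure HRQoL at baseline and at 6, 12, 18, 24, 30 and 36-months post-randomisation", and the resource-use questionnaire follows the same schedule. On the effect side, "QALYs will be calculated using the area under the curve approach", and "All costs and effects will be discounted at 3.5% following NICE guidelines".

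The intervention being costed has the same length: "the structured follow-up includes clinical reviews, CT scans and endoscopy for up to 36 months". The decision rule is then stated: "The ICER will be compared against the threshold used to establish value for money in the NHS", which section 20.12 puts at about £20,000 to £30,000 per QALY. The net monetary benefit from the bootstrap replicates is evaluated over threshold values in the same way. The one sensitivity analysis described is a societal perspective. A closing sentence promises a robustness check without giving its content.

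The design effect is in section 20.2: "an expected all-cause 3-year mortality in the control group of 55% and an assumed improvement to 45% in the intervention group", with a hazard ratio of 0.749 under proportional hazards. Vital status is followed for longer than costs and utilities. Section 10.3 says "Mortality and recurrence data will be collected for 36 months after the last participant is randomised". Section 20.12 does not say whether those later data enter the economic analysis.

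**The concern.** Costs and benefits of surveillance do not fall in the same period. Every scheduled CT scan, the endoscopy and all scheduled reviews take place by month 36. The hoped-for benefit is longer survival. If the trial meets its target, ten more people per hundred are alive when the QALY count stops, and their later life adds nothing to the denominator of the ICER.

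This matters because cost-effectiveness is a stated objective (section 9.3). Section 8 lists cost among three barriers to intensive surveillance, and section 28 expects the results to feed into NICE guidance. A short-horizon ICER would be the only figure the protocol commits to setting against the NHS threshold.

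**Working it through.** **Inputs.** From section 20.2: 3-year mortality 55% (control) and 45% (intervention), hazard ratio 0.749, 90% power, two-sided alpha 0.05, 273 + 229 = 502 deaths, 3 years' recruitment plus 3 years' follow-up. From section 20.12: discount rate 3.5%. The protocol gives no unit costs, no utilities and no survival after month 36, so those are assumptions below.

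**The plan's own figures.** HR = ln(0.55)/ln(0.45) = 0.7487, which agrees with 0.749. Schoenfeld's formula with this HR, 90% power and two-sided 5% gives 502 deaths, also as stated.

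**Gain inside the window.** The protocol assumes proportional hazards; constant hazards are my simplification. They are −ln(0.45)/3 = 0.2662 and −ln(0.55)/3 = 0.1993 per year. Mean life-years to year 3 are (1 − 0.45)/0.2662 = 2.066 and (1 − 0.55)/0.1993 = 2.258. The gain is 0.192, or 0.180 discounted.

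**Gain after the window, hazards still proportional.**
- Years 3 to 6 (the 3 + 3 years of the sample-size calculation) add 0.312 (0.267 discounted). Share inside the window: 0.192/(0.192 + 0.312) = 38% (40% discounted).
- Over a lifetime the gain after month 36 is 1.069 (0.773 discounted). Share: 0.192/1.261 = 15% (19% discounted).

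**Gain after the window, hazards equal from month 36.** The extra 10% of survivors add 0.10 × L, where L is their assumed mean further life.

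| L (years) | Gain after month 36 | Share counted | Share counted, discounted |
|---|---|---|---|
| 1 | 0.10 | 66% | 67% |
| 2 | 0.20 | 49% | 52% |
| 5 | 0.50 | 28% | 32% |
| 10 | 1.00 | 16% | 21% |

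Half the gain is counted at L = 0.192/0.10 = 1.9 years (2.1 discounted). If instead the curves converge linearly over T years, the later gain is 0.10 × T/2. The share is then 66%, 49% or 28% for T = 2, 4 or 10.

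**Direction of the ICER.** Let C be the within-trial incremental cost, w = 0.180 the discounted gain inside the window, b the discounted gain after it, k the cost per added life-year after month 36, and u a utility common to both periods.
- Within-trial ICER = C/(u × w).
- Longer-horizon ICER = (C + k × b)/(u × (w + b)).
- The first exceeds the second only if k < C/w = 5.56 × C.

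For assumed C of £2,000, £3,000 or £5,000 the limit on k is about £11,100, £16,700 or £27,800 per life-year. As an example, take C = £3,000, u = 0.75 and L = 5 (b = 0.385). The within-trial ICER is 3,000/(0.75 × 0.180), about £22,200. The longer-horizon ICER is about £8,900 at k = £2,000, £20,700 at k = £15,000 and £29,800 at k = £25,000.

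**The case against.** The strongest reply is that nothing here is misstated. The analysis is openly labelled within-trial and would validly estimate what that label says. A separate health economics analysis plan is named in section 28 but is not at hand, and it may add a longer horizon. Section 20.12 also commits to good-practice guidance and leaves its robustness analyses open. A reader might infer that the protocol rules out extrapolation, or excludes deaths after month 36 from the economic analysis. It says neither; it is silent. What remains is that section 20.12 itself fixes one horizon and one threshold comparison, and that this horizon suits a survival-driven intervention poorly.

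Other tempting readings also go too far:

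- **The ICER is certainly biased upwards.** The window omits later costs as well as later benefits. The hoped-for mechanism is earlier treatment of recurrence, so the extra survivors may include people on costly treatment with short further life. The working shows that the sign can change.
- **A fixed fold-overstatement.** Inverting the discounted shares for L between 3 and 10 years gives about 2.4 to 4.7. That holds only with equal hazards after month 36 and essentially no later cost difference, neither of which the documents establish.
- **The window closes where the curves are furthest apart.** Under constant hazards the gap peaks at ln(0.2662/0.1993)/(0.2662 − 0.1993), about 4.3 years.
- **Every cost caused by surveillance is counted.** Scheduled surveillance is. Treatment of recurrences found on the scans at months 30 and 36 falls partly or wholly after the last resource-use collection.
- **The 36-month ICER should not be set against the threshold.** That is a reporting preference, and the documents give no ground for barring the comparison.

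**Conclusion.** The concern holds as a poor fit between the stated method and the question, not as an error of calculation. At the design effect, most of the life-years gained fall after month 36 if hazards stay proportional and constant. With equal hazards afterwards this still holds unless the extra survivors live on average less than about 2 more years, or the curves converge within about 4 years.

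An overstated ICER is the more likely direction if the benefit persists and later care is modest in cost. Section 20.3 gives some support: about 90% of recurrences occur within 3 years of surgery, so much of the recurrence treatment should start inside the window. The size cannot be fixed from the documents, because post-36-month survival, unit costs and utilities are all assumed here. If surveillance does not change survival, this bias does not arise.

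**What to change.** Keep the within-trial analysis and its comparison with the threshold. Add to section 20.12, with the detail in the health economics analysis plan, a pre-specified analysis with a longer or lifetime horizon that:

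- uses all mortality and recurrence data collected up to 36 months after the last randomisation (with 32 months' recruitment, the earliest entrants have up to 32 + 36 = 68 months);
- includes both costs and utilities after month 36 by recurrence status, informed by the values observed in the trial;
- gives scenarios for how long the survival effect lasts, including convergence of the curves, and for residual survival;
- reports its ICER beside the within-trial one.

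The cost is modelling work by the health economists and a short protocol amendment. No extra participants or data collection are needed. The drawback is that the longer-horizon result will depend on extrapolation assumptions, which is why it should be shown as scenarios next to the observed 36-month result.
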